## A1. Predicting the Risk of Lung Cancer.

Lung cancer screening is most effective when applied to people at high risk. The use of an accurate risk prediction model that incorporates risk factors besides age and smoking history is more efficient at identifying people who will develop lung cancer and die from the disease and will likely lead to a more cost-effective screening program (lung cancers deaths averted per screen) than the NLST criteria.

Currently, at least 17 lung cancer risk prediction models exist. These risk models have been summarized by in a recent publication. The [name] PLCOm2011, PLCOm2012 and PLCOall2014 models and the Hoggart European Prospective Investigation into Cancer and Nutrition (EPIC) model are the only models that are based on large prospectively followed population-based samples not limited to people at high risk of lung cancer and they show high discrimination and calibration in smokers.

Quesionnaire-based approaches do not require direct contact because risk can be assessed by telephone or online. This approach is relatively simple, has broad coverage, and is less time consuming and costly than the clinic-based approach that requires direct contact with the participants. When the threshhold for screening in the PLCOm2012 prediction model was set to give the same proportion screened from the PLCO trial as the NLST criteria, it had 11.9% (p<0.001) greater sensitivity (83.0% vs 71.1%) in identifying those who would be diagnosed with lung cancer in six years of follow-up and 41.3% fewer future lung cancers were missed (17.0% vs 28.9%). Using an earlier version of the PLCOm2011 risk assessment tool for recruitment of participants into the Pan-Canadian Early Detection of Lung Cancer Study, the risk prediction tool was found to be very accurate. The average six-year lung cancer risk in 2,537 participants recruited in 8 centers across Canada was 4.5%. The percentage of confirmed lung cancer cases was 6.5% after a median follow-up of 3.8 years. In a subsequent study,

[name] and colleagues estimate from the PLCOm2012 risk prediction model that a threshold of 1.51% for 6-year lung cancer risk (65th percentile of risk) can identify 80% of ever smokers who will

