C13.3 To determine the incremental value of air pollution for lung cancer risk assessment versus the PLCOm2012 model, newly diagnosed lung cancer patients (both ever-smokers and never-smokers) and the Lung Screening Study participants (ever-smokers) in the Vancouver site will be used to test if there is a significant difference in the pollution index between those with and without lung cancer and those who meet the PLCOm2012 6-year lung cancer risk threshold ≥0.0151 versus those who don't. We will externally validate any resultant risk prediction model using the Canadian Partnership for Tomorrow Project (CPTP) cohorts, the Canadian Communities Health Survey (CCHS) data linked to provincial cancer cancer incidence registries (Table 2), as well as the on-going 10,000 screening cohort from the National Taiwan University to determine the predictive performance (discrimination and calibration) of the model overall, and where numbers permit, in subsets and ethnic subgroups of the population. The CPTP and CCHS data linked to cancer registry outcomes provide ideal data for our efforts to validate the PLCO risk models and lung cancer screening selection criteria in Canadian settings, and to

potentially improve them. These data include prospective follow-up data which provide estimation of true risks based on incidence data (probability of lung cancer in a defined population at risk per defined time period).

We anticipate well over 1,700 lung cancers from the CPTP and CCHS cohorts. To minimize over-fitting of any new model, a rule of thumb suggests that 10-20 outcomes be present per predictor variable in the model. We expect all new models to have 15 or fewer predictors and thus do not expect serious problems with over-fit. We will also use bootstrap methods to estimate model *optimism*.

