If the PLCOm2012 model performs in the Canadian population as well as in the PLCO cohort (AUC 0.80), it may be difficult to find significant incremental improvement in AUC from the addition of new predictor(s) to the model. Net Reclassification Improvement (NRI) is a method that is more sensitive at identifying prediction improvements at important decision-making thresholds. The NRI has been criticized recently and as a response it has been recommended that the number of risk categories for decision-making be kept small and risk boundaries are clinically relevant. We will apply these guideline in our application of NRI.

The predictive performance of the PLCO models will be assessed by AUC, a measure of discrimination or ability to classify correctly, and assessing calibration (do model-estimated probabilities correspond to observed probabilities). Calibration will be evaluated graphically by plotting observed risk versus model-estimated risk by deciles of model risk. Calibration will also be evaluated by assessing the magnitude of the mean and 90th percentile absolute error (observed minus predicted risks), and by applying Cox recalibration (logistic recalibration). The efficiencies of the PLCOm2012 risk ≥0.0151 and the USPSTF criteria to select high risk smokers for LDCT screening will be compared by applying these criteria to the prospective data and determining the number that are criteria-positive, sensitivity, specificity and PPVs. Confidence intervals for proportions will be prepared using the exact binomial method. Statistical measures of performance fail to estimate clinical benefit of one method over another. We will apply *decision curve anaysis* to compare net benefit diferences between the diferent models and criteria.

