**Table 2. Ever Smoker Population Cohorts for Evaluation of Additional Risk Factors** 

	СРТР	сснѕ
Numbers	48,504	71,514
Male: Female	46%:54%	NA
Ethnicity White Non-white	94%	NA
Current: Ex Smokers	17%:83%	39%:61%
Education  ≤HS  ≥ College	28% 72%	52% 48%
Projected # lung cancers for analysis in 3 years	1,000	770

CPTP = Canadian Partnership Tomorrow Generation Project

CCHS = Canadian Community Health Survey

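### C13.3 adopts NRI as more sensitive than AUC, but with few categories and the plan's own inputs it has less power than AUC and can react to miscalibration

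*Protocol*

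**What the plan says.** C12 and C13.3 of the protocol ask whether air pollution, or another new predictor, improves on PLCOm2012 in identifying people for screening. C13.3 expects that, if PLCOm2012 keeps its AUC of 0.80 in Canada, "it may be difficult to find significant incremental improvement in AUC from the addition of new predictor(s) to the model". The next sentence offers the alternative: "Net Reclassification Improvement (NRI) is a method that is more sensitive at identifying prediction improvements at important decision-making thresholds". The protocol notes that NRI has been criticised and commits to the recommended response, that "the number of risk categories for decision-making be kept small and risk boundaries are clinically relevant". This is a categorical NRI. The only decision threshold that C13.3 names is the "PLCOm2012 6-year lung cancer risk threshold ≥0.0151".

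On data, C13.3 states "We anticipate well over 1,700 lung cancers from the CPTP and CCHS cohorts". Table 2 gives the breakdown by cohort under "Projected # lung cancers for analysis in 3 years".

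C13.3 also plans calibration plots, absolute prediction error, logistic recalibration and decision curves. Logistic recalibration is listed as a way of evaluating calibration, not as a step to take before reclassification is counted. The one significance test named in C13.3 compares the pollution index between people with and without lung cancer, and between those above and below the threshold. It is not stated to be conditional on PLCOm2012 risk.

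**The concern.** Because the sentence on NRI directly follows one about finding a significant gain, it reads as a claim about power. A categorical NRI counts only people who cross a cut-off, so it discards most of the information in a new predictor. One would expect it to be less powerful than the AUC difference, and much less powerful than a test of the predictor itself.

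NRI also responds to anything that moves people across the cut-off, including a difference in calibration between the two models. A significant NRI could then be reported as added value when the new model has only been refitted to local data.

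At stake is the answer to the air-pollution sub-study: a real effect could be passed over, or recalibration taken for an effect.

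**Working it through.** **Inputs from the protocol.** Baseline AUC 0.80 and cut-off 0.0151 (C13.3). Cancers: 1,000 + 770 = 1,770, which reproduces the statement of over 1,700 and exceeds it by 70/1,700 = 4.1%. Ever smokers: 48,504 + 71,514 = 120,018 (Table 2). Event rate: 1,770/120,018 = 1.47%. The protocol states no power for NRI or AUC, so there is no such figure to reproduce.

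**Assumptions.** Two-sided 5%, as stated for C13.1. Binormal scores. A pollution index independent of the PLCOm2012 score. Odds ratios (OR) per SD over a range, because the exposure SD is not given. A4 cites an OR of 1.29 per 10 µg/m³; if the SD were 2 to 5 µg/m³, that is 1.29^0.2 = 1.05 to 1.29^0.5 = 1.14 per SD.

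**Simulated power**, 1,770 cancers and 118,248 non-cases, 300 replicates. The extra cut-offs of 3% and 1% are assumptions.

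| OR per SD | NRI, 2 categories | NRI, 3 | NRI, 4 | AUC difference (DeLong) |
|---|---|---|---|---|
| 1.105 | 7% | 7% | 10% | 43% |
| 1.162 | 11% | 16% | 28% | 76% |
| 1.221 | 18% | 35% | 56% | 92% |
| 1.284 | 29% | 60% | 80% | 99% |

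Further runs of 100 to 200 replicates, with small differences in set-up, kept the same ordering. Across set-ups the two-category NRI against AUC is roughly 4–7% against 32–43% at an OR of about 1.10, and 12–19% against 88–100% at about 1.20. The test of the pollution term has 97–99% at about 1.10 and 100% at about 1.20.

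**Hand check, coefficient test at OR 1.105 (ln OR = 0.10).** SE ≈ 1/√(1,770 × 118,248/120,018) = 1/√1,743.9 = 0.0239. z = 0.10/0.0239 = 4.18. Power = Φ(4.18 − 1.96) = 98.7%.

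**Hand check, two-category NRI.**
- The score separation is d = √2 × Φ⁻¹(0.80) = 1.190.
- The cut-off lies at x = [logit(0.0151) − logit(0.01475) + d²/2]/d = 0.615 on the non-case scale.
- The density of cases there is φ(0.615 − 1.190)/1.190 = 0.284 per logit.
- The share of cases crossing is about 0.284 × ln OR × √(2/π). At OR 1.105 this is 2.3%, so SE ≈ √(0.0227/1,770) = 0.0036. The mean simulated NRI is 0.0010, so z = 0.28 and power is about 5%.
- At OR 1.221, 4.5% cross, SE ≈ 0.0051 and NRI = 0.0052. So z = 1.02 and power is about 17%.

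Both agree with the simulation.

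**Where the gap narrows.** With 1,770 cancers at a 3.9% event rate (the six-year mean risk in C13.1), two-category NRI against AUC is 11% against 38% at OR 1.105 and 86% against 99.5% at 1.284. With 155 cancers in 4,000 it is 13% against 18% at 1.22 and 44% against 55% at 1.49.

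**No pollution effect, published PLCOm2012 left as it is, new model refitted.** If the published model is off by the factor observed/expected (O/E), everyone who changes category moves in the same direction. At O/E 1.44 its cut-off shifts to 0.615 + ln(1.44)/1.190 = 0.922. Between the two cut-offs lie 11.1% of cases and 9.1% of non-cases, so NRI = 0.021. SE = √(0.111/1,770 + 0.091/118,248) = 0.0080, z = 2.58, and rejection is about 73%. Simulations gave 75–83%. At O/E 1.2 the same formula gives 18%, and simulations gave about 13–15%. With both models calibrated, rejection is about 5%. At a 3.9% event rate, odds errors of 20–25% gave a significant NRI, in one direction or the other, in every run.

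**The case against.** The strongest reply is that C13.3 never makes NRI the significance test. It sets no null hypothesis, alpha or decision rule for it, and a coefficient test could be left to the analysis plan. That stands: a reader might infer a designated test that would decide the sub-study, and the text does not go that far. What remains is a stated reason for choosing a method, and that reason is wrong for the form chosen.

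Second, the protocol qualifies its claim by reference to decision thresholds, and C12 is about selection for screening. Low NRI power might be read as pure loss of information. It is not: under these assumptions the true NRI is only about 0.001 to 0.009 over the ORs examined, so selection barely changes. A coefficient test detects association, not better selection.

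Third, C13.3 does not fix two categories, and more categories help. A category-free NRI would in fact beat AUC (about 93% against 43–46% at OR 1.105), but the protocol commits to categories. The 1.47% event rate also sets a three-year cancer count against a six-year risk threshold.

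Fourth, a reader might infer that the plan will produce false positives. That requires an unrecalibrated PLCOm2012 comparator, which the protocol neither states nor excludes. Nor is 1.44 an estimate for these cohorts. It is 6.5/4.5 from section A1, where "The percentage of confirmed lung cancer cases was 6.5% after a median follow-up of 3.8 years" and the 4.5% is a six-year prediction from an earlier model. The planned calibration checks would make miscalibration visible, but nothing ties them to the NRI.

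**Conclusion.** The point holds in limited form. The stated reason for preferring NRI is incorrect for a few-category NRI at AUC 0.80, about 1,770 cancers in 120,018 ever smokers and the 0.0151 cut-off. It is less powerful than the AUC difference at every OR examined where power was not already near 100%, and far less powerful than a test of the predictor given PLCOm2012 risk. The group comparison in C13.3 does not fill that place, because it is not conditional on PLCOm2012 risk.

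The calibration problem is conditional: it arises only if the published model is compared without recalibration, and its size depends on assumed O/E ratios. The power figures rest on binormal scores, an independent pollution index and assumed ORs per SD, with a Monte Carlo error of a few percentage points.

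The documents do not support saying that the sub-study will miss a pollution effect or report a false one. The sub-study is optional and neither primary objective is affected. The passage should be corrected, but it does not endanger the main study.

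**What to change.** In C13.3:

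- Delete the rationale that NRI is the more sensitive method.
- State that incremental value is tested by a likelihood-ratio or Wald test of the new predictor in a logistic model containing the PLCOm2012 linear predictor.
- Require that PLCOm2012 be recalibrated (intercept and slope) in the same data before any reclassification is counted.
- Report AUC change, NRI (event and non-event parts separately, with intervals) and the planned decision curves as descriptive measures of whether selection improves.

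The cost is a wording change and one extra model fit on data already planned. The downside is that a significant term may be too small to change who is selected, so the descriptive measures must be read beside the test.

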# C14. Health Economics Analysis

## C14.1 Lung Cancer Natural History Model

The economic analysis will be undertaken with the use of a natural history microsimulation model of lung cancer that is being developed in parallel with the LDCT trial by [name] and her team at Cancer Council NSW (CCNSW). The development of the lung cancer model is part of a broader and separate program of work and will serve as tool for assessing the outcomes of the LDCT trial. The CCNSW team has successfully built and implemented a natural history model for cancer of the cervix, which was used to evaluate the effectiveness of different cervical screening interventions within the framework of a screening trial in the UK. Similar methodology will be used to assess the effectiveness and cost-effectiveness of the proposed LDCT screening strategies for this trial.

Specifically, a lung cancer natural history model will be constructed to simulate lung cancer incidence and mortality in the Australian population and will be built, validated, and calibrated using representative datasets, and a large, population-based Australian cohort study (the 45 and Up Study).81 It will be an individual-based (microsimulation) model developed using a discrete-event simulation framework implemented in C++ and will consist of several core components (e.g., lung cancer natural history, diagnosis, treatment, and survival), including a 'smoking history generator'. The smoking history generator will simulate individual life/smoking histories and will be similar to that developed by the National Cancer Institute's Cancer Intervention and Surveillance Modelling Network (CISNET) that serves as input for similar lung cancer models in the US.82,83 CISNET (http://cisnet.cancer.gov) is a consortium of investigators that uses mathematical modeling to assess the impact of cancer control interventions on population trends in incidence and mortality for a variety of cancer sites, and the team at CCNSW is currently a member (for cervical cancer). Although detailed tobacco exposure by age, sex and birth cohort will not be simulated for the Canadian, Italian and Danish trial participants, the model will be adapted for these sites to incorporate historical tobacco exposure for each country as previously done for CISNET. Specifically, published data for the US-CISNET model will be used in conjunction with a review of smoking in each country, to adapt the background and tobacco exposure assumptions in the trial population.

To assess the effectiveness of the various screening strategies within the trial, a simulated cohort of individuals who match trial participants (age, smoking status, etc.) will be configured. As trial data become available ( $T_0$ ,  $T_1$ ,  $T_2$ ), successive validation exercises will be performed using the demographic, participation, cost, and outcomes data from trial participants. The modelled health resource utilisation and health outcome predictions for the simulated cohort will be compared to the

observed data as in previous work. Following completion of this validation step, and in order to perform health economic evaluation of LDCT screening as performed in the trial, projections of 10-year and lifetime outcomes and costs for trial participants will then be performed.

#### C14.2 Ascertaining cost data

Health care resource utilization rates within the trial will be prospectively reported from each of the study centres via an electronic case report form. The method of capturing direct medical costs will vary depending on the setting. In Australia, costs will be ascertained from utilisation data within the trial, including the costs of screening itself, out-of-hospital medical services funded under the Medicare Benefits Schedule and/or the Department of Veteran Affairs, public hospital utilization, and patient diaries as per the Queensland Lung Cancer Screening Study. Other Australian datasets, such as the 45 and Up Study, will be used to supplement these cost data with information regarding emergency department presentations, private hospital admissions, and prescription pharmaceuticals subsidised by the Pharmaceutical Benefit Scheme.

Societal cost data will be ascertained from questionnaires administered to a subgroup of participants and to consenting lung cancer patients receiving treatment at the BC Cancer Agency. The questionnaires will be used to calculate costs to screening participants and will be calculated on a pervisit basis with consideration to the average travel time, distance and modality used to attend screening or non-curative treatment appointments in Vancouver, BC or in Australia as well as the employment status and out-of-pocket expenses to attend screening or lung cancer treatment appointments.

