# **C5.0 Optional Sub-Study at the Vancouver Site**

The modified Pan-Canadian Early Detection of Lung Cancer risk assessment questionnaire (Figure 2) plus an outdoor and domestic air pollution exposure questionnaire (Appendix 1) will be administered to all newly diagnosed lung cancer patients (estimated to be 1,400 patients over two years) who will be attending the Vancouver Cancer Center of the BC Cancer Agency or the Thoracic Surgery Department of the Vancouver General Hospital (VGH). The VGH Thoracic Surgery Unit is one of four thoracic surgery centers for surgical treatment of lung cancer patients in the entire 4.6 million population in British Columbia. From the risk assessment tool, we will determine the relative sensitivity of the PLCOm2012-risk ≥1.51% threshold versus the USPSTF screening criteria to identify lung cancer patients who are ever smokers.

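### C14.2 collects patient travel and time for screening and non-curative visits only, so travel to curative treatment is missing from the societal cost data

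*Protocol*

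**What the plan says.** Protocol C14.2 separates two kinds of cost.

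- **Direct medical costs.** "Health care resource utilization rates within the trial will be prospectively reported from each of the study centres via an electronic case report form". Nothing limits this by treatment intent.
- **Societal costs.** These come from "questionnaires administered to a subgroup of participants and to consenting lung cancer patients receiving treatment at the BC Cancer Agency". On the unit of costing, C14.2 says: "The questionnaires will be used to calculate costs to screening participants and will be calculated on a pervisit basis".

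One sentence then fixes which visits the societal items cover, and it uses two scopes:

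- average travel time, with "distance and modality used to attend screening or non-curative treatment appointments in Vancouver, BC or in Australia";
- for patients' employment status and own spending, a second and wider scope: "out-of-pocket expenses to attend screening or lung cancer treatment appointments".

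The first scope stops at non-curative treatment. The second covers lung cancer treatment of any intent. C14.2 does not explain the difference.

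**The concern.** A screening programme is meant to produce curative treatment. C9 states that work-up of a suspicious nodule should end in a diagnosis and definitive treatment, and C11 makes resection rate and stage distribution outcomes. The visits left out of the travel items are therefore ones the programme is designed to generate.

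Cost-effectiveness also carries weight in this protocol. The Project Summary opens with it, A2 argues from cost per QALY, and C14.1 plans projections of 10-year and lifetime costs. A gap in a cost input that tends to fall on one side of the comparison deserves correction.

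This is a limit on what is collected, so an analysis plan could repair it only in part. Travel details not asked at the time would have to be recalled later or imputed, and C14.2 gives no rule for carrying travel from screening visits over to curative visits.

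**Working it through.** The protocol states no figure for this component, so there is nothing to reproduce. The check compares scopes.

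**Step 1. What each item covers**

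| Item | Screening visits | Non-curative treatment | Curative treatment | Source |
|---|---|---|---|---|
| Travel time, distance, modality | yes | yes | not named | C14.2 |
| Employment status, out-of-pocket expenses | yes | yes | yes | C14.2 |
| Direct medical resource use | yes | yes | yes | C14.2 |
| Count of outpatient visits for lung cancer diagnosis or treatment | not applicable | yes | yes | C11 |
| Treatment procedures, length of stay, ward type | not applicable | yes | yes | C11 |

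Only one cell is empty: travel and time for curative treatment. No other section fills it. C11 counts the visits but does not collect the travel.

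**Step 2. What the empty cell does to a comparison**

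Let V_cur be curative-treatment visits per person under a strategy, and c the travel and time cost per visit. The amount missing from the cost difference is

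Δ = (V_cur under LDCT − V_cur under the comparator) × c.

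- If screening adds curative visits, Δ > 0 and the measured societal cost difference is too low by Δ.
- If screening also averts non-curative visits, that saving is rightly credited. The curative visits that offset it are not debited. The error remains Δ, but the measured travel difference could then show a saving where there is none.
- If screening adds no curative visits, Δ = 0 and the comparison is not affected.

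**Step 3. Size**

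The protocol gives neither factor of Δ: no curative visits per person and no cost per visit. The size cannot be stated. The 155 cancers expected among 4000 participants in C13.1 do not help. Turning them into curatively treated patients needs an assumed share, a count of patients is not a cost, and the questionnaires go to only a subgroup of participants.

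**The case against.** The strongest reply is that this is an inconsistency of wording with little behind it. Much of that stands.

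- **Most of the curative burden is captured.** A reader might infer that the cost of curative treatment is left out altogether. The protocol does not support this. Direct medical use, outpatient visit counts, procedures and length of stay are recorded whatever the intent, and out-of-pocket expenses cover all lung cancer treatment appointments. Those expenses may include fares, which narrows the gap further.
- **Nothing is set to zero.** C14.2 plans average costs per visit, and C11 supplies visit counts regardless of intent. An analyst could apply a travel average to curative visits. C14.2 does not say that this will be done, and it would assume that travel to treatment resembles travel to screening or non-curative care.
- **Respondents are not only cancer agency patients.** A reader might infer that surgical patients are missed, because one respondent group is "consenting lung cancer patients receiving treatment at the BC Cancer Agency" while C5.0 says "The VGH Thoracic Surgery Unit is one of four thoracic surgery centers for surgical treatment of lung cancer patients". That does not follow. A subgroup of participants is also questioned, Australia is named beside Vancouver, and the protocol does not say that the agency gives no curative treatment.
- **The overall ratio is not shown to be biased.** It is tempting to conclude that LDCT looks cheaper than it is. C14 names no comparator for a cost-effectiveness ratio. The trial's main contrast is between two selection rules, with no unscreened arm. The direction holds only for this component, and only against a comparator with fewer curative visits.
- **Health economics is not among the numbered objectives** in sections 1.0 and 2.0. This limits the weight of the point.

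What the reply does not remove is the empty cell. Under the protocol as written, travel time, distance and modality for curative visits are not collected, and no reason is given.

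**Conclusion.** The point holds for one component. C14.2 restricts the travel items to screening and non-curative treatment, while the other societal items in the same sentence cover all lung cancer treatment. Patient travel and time for curative treatment are therefore not measured.

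The size is unknown and cannot be derived from the protocol. The direction is conditional: if screening leads to more curative visits than the comparator does, the societal cost of LDCT is understated. That condition is plausible given the aim of work-up in C9, but the protocol does not establish it. The conclusion rests on reading C14.2 literally and on no other section supplying the missing travel data.

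It is a modest defect. It should still be corrected, because it can favour the intervention, is hard to repair after data collection and costs almost nothing to remove.

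**What to change.** In C14.2, change the scope of the travel items to *screening or lung cancer diagnostic and treatment appointments, curative and non-curative*. Use the same phrase for the out-of-pocket items, so that both have one scope and diagnostic visits are explicitly included in each. State that the per-visit travel cost will be applied to all the lung cancer outpatient visits already recorded under C11. If the restriction to non-curative visits is deliberate, give the reason and the likely direction of its effect.

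Offering the cost questionnaire at the Vancouver General Hospital thoracic surgery clinic as well is an optional extension and is not needed to close the gap.

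The cost is a few more questionnaire items and possibly a slightly less favourable cost-effectiveness figure. Visit counts need no new collection.
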